1.1 Research Objectives and Significance

Acute lung injury (ALI) and the more severe acute respiratory distress syndrome (ARDS) are common postoperative complications of major liver surgery and liver transplantation, closely associated with significantly increased patient morbidity and mortality. Early warning systems based on interpretable machine learning models can identify abnormalities based on past patterns and current observations, issuing warning signals before hazards occur. These systems are considered highly valuable for precise prediction of clinical complications like ALI, which have sudden onsets and lack specific predictive indicators. This study aims to develop interpretable machine learning models using digital and intelligent methods, with cardiopulmonary interaction parameters as key features, to predict ALI in the perioperative period of liver surgery. Further, by integrating expert systems and iteratively optimizing them using information fusion technology, we aim to construct a digital and intelligent early warning system for ALI throughout the entire liver surgery process, meeting specificity and accuracy requirements and enabling early detection of high-risk ALI patients. Ultimately, we aim to establish an integrated platform for prevention, diagnosis, and treatment of ALI throughout the liver surgery process, centered on the ALI early warning system. This platform is designed to provide robust clinical decision support for healthcare professionals, reducing the incidence and mortality of ALI in the perioperative period of liver surgery.

1.2 Domestic and International Research Status

Domestic Research Status: While some progress has been made in ALI research for liver

surgery in China, large-scale clinical studies and effective predictive models remain insufficient.

International Research Status: ALI research for liver surgery is relatively advanced abroad, but challenges in predictive accuracy persist.

1.3 Research Conditions at Our Hospital

Data Resources: Beijing Tsinghua Changgung Hospital boasts rich clinical data resources, including a medical data center, electronic medical record systems, laboratory information systems, etc., providing ample data support for the research.

Technical Equipment: The hospital is equipped with advanced medical devices and technologies to meet data collection and analysis needs.

Professional Team: The research team comprises members with extensive clinical and research experience to ensure smooth research progress.

1. Research Objectives and Content

1.1 Research Objectives

Acute lung injury (ALI) and the more severe acute respiratory distress syndrome (ARDS) are common after major liver surgery and liver transplantation, and are closely linked to significantly increased patient morbidity and mortality. Severe liver dysfunction can lead to hemodynamic changes, coagulation abnormalities, and immune dysregulation, all of which can increase the risk of perioperative pulmonary complications, particularly ALI. Given the continuous and dynamic nature of ALI's pathophysiological process and its typically sudden onset, early warning systems are crucial. Such systems identify abnormalities based on past patterns and current observations, issuing warnings before hazards occur. A comprehensive early warning system can provide more effective perioperative coverage and clinical protection.

This study aims to develop interpretable machine learning models using digital and intelligent methods, focusing on ALI prediction in the perioperative period of liver surgery. It also aims to construct an ALI early warning system for the entire liver surgery process and establish an integrated ALI diagnosis and treatment platform for the entire liver surgery process, centered on the ALI early warning system. This platform will provide strong clinical decision support for medical professionals, with the goal of reducing the incidence and mortality of ALI in the perioperative period of liver surgery.

1.2 Research Content

1.2.1 Construction and Validation of Interpretable Machine Learning Models

Data Collection and Preprocessing

Literature Review: Systematically review domestic and international literature to understand the pathogenesis, risk factors, clinical manifestations, and pros and cons of existing predictive models for acute lung injury (ALI). This will provide a theoretical basis for data collection and model construction in this study.

Data Collection: Collect perioperative data from patients aged 18 and above who underwent major liver surgery at Beijing Tsinghua Changgung Hospital between June 2019 and May 2024. The data includes cardiopulmonary interaction parameters (e.g., pulse pressure variation, systolic pressure variation, stroke volume variation), preoperative baseline information (age, gender, weight, medical history), intraoperative information (surgery type, duration, anesthesia method, blood transfusion status), and postoperative information (complications, hospital stay, follow-up status).

Feature Selection: Use univariate and multivariate analyses to select features strongly associated with ALI occurrence as input variables for the machine learning (ML) model.

Model Development

Algorithm Selection: Develop interpretable ML models using six algorithms, including logistic regression, random forest, support vector machines, and neural networks, to enhance model accuracy and generalization.

Model Training: Split the dataset into training and validation sets. Train the model using the training set and optimize parameters through cross-validation to prevent overfitting.

Model Simplification and Optimization

Feature Importance Assessment: For the best-performing ML model, calculate the Shapley Additive Explanations (SHAP) values of input features to evaluate their importance.

Model Simplification: Select the top 20 features based on SHAP values to create a

simplified risk prediction model, improving interpretability and practicality.

Feature Weight Determination: Determine the feature weights in the simplified model for the entire major liver surgery process to support clinical decision-making.

Model Validation and Evaluation

Independent Test Set Validation: Validate the accuracy of the ML model using an independent clinical test set and evaluate its predictive performance using metrics such as sensitivity, specificity, accuracy, and ROC curve.

Interpretability Analysis: Conduct an interpretability analysis of the model's predictions, explaining the decision-making process and prediction basis to enhance clinical acceptance.

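### The association filter placed ahead of the six algorithms can drop useful predictors, including the cardiopulmonary parameters named as key features, before any model is trained

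*Protocol*

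**What the plan says.** Protocol section 1.2.1, Feature Selection, applies univariate and multivariate analyses to "select features strongly associated with ALI occurrence as input variables for the machine learning (ML) model". The step sits under data collection and preprocessing. It is listed before the choice of algorithms and before the split into training and validation sets.

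The surviving features feed "six algorithms, including logistic regression, random forest, support vector machines, and neural networks". Three of the four named methods (random forest, support vector machine, neural network) can represent non-linear effects and interactions.

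A second reduction follows. SHAP values are computed for the inputs of the best model, and the instruction is "Select the top 20 features based on SHAP values to create a" simplified model.

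The section on research objectives and significance describes the models as built "with cardiopulmonary interaction parameters as key features, to predict ALI in the perioperative period of liver surgery". Section 1.2.1 lists pulse pressure variation (PPV), systolic pressure variation (SPV) and stroke volume variation (SVV) as examples of these parameters. No section exempts them from the filter.

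**The concern.** Flexible learners are included because effects may be curved or may depend on other variables, but they can use only what they are given. A filter that judges each feature by its association with the outcome, if run with linear terms, discards a predictor whose marginal trend is close to zero, however much it contributes in another form.

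The multivariate part adds a separate risk. Measures of the same physiology may be strongly correlated. In a joint model they share their signal, and each can miss a significance threshold even though together they predict well.

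The stake is the study's premise. If PPV, SPV or SVV are absent from the final model, the report could not say whether they failed to predict or never reached the models. The comparison of algorithms would also be made on inputs already shaped by the filter.

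**Working it through.** **Inputs.** The event rate is 4.1% (section 2.3). The size of the retrospective dataset is not stated, so N = 1,000 to 3,000 is assumed, which gives 1,000 × 0.041 = 41 to 3,000 × 0.041 = 123 events. The protocol gives no threshold for the filter; p < 0.05 is assumed. All effect sizes below are assumptions.

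**The plan's own figures.** None bears on the filter. As a check on the event rate, the O/E row of the sample size table follows from n = (1 − p)/(p × SE²) = 0.959/(0.041 × 0.245²) = 389.7, rounded up to 390 as stated.

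**Step 1: effect shapes under a linear-term screen.** Each dataset has a standard normal x and an intercept set to give 4.1% events; 600 replicates. The table gives the share in which x is kept over N = 1,000 to 3,000. The multivariable model has main effects only and includes all candidates.

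| Shape of effect | True AUC | Univariate | Multivariable |
|---|---|---|---|
| Linear, 0.5x | 0.64 | 86–100% | 86–100% |
| One subgroup only, 0.7x·g | 0.62 | 64–97% | 65–97% |
| Symmetric U, 0.5x² (x² capped at 9) | 0.72 | 20–26% | 20–26% |
| Crossover, 0.7x(2g − 1) | 0.69 | 9–10% | 9–10% |
| Suppressed, 0.6x − 1.0w, with w correlated 0.6 with x | 0.71 | 3–6% | 81–100% |

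Here g is a binary variable with prevalence 0.5. Linear and one-subgroup effects mostly survive. A main-effects multivariable model rescues the suppressed predictor, but not the U-shaped or crossover one, and a larger N does not help those two.

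**Step 2: how fragile the U-shape result is.** Log-odds = a + 0.5(x − c)², N = 2,500, 400 replicates, share kept at p < 0.05:

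| Shift c | t-test | Rank test | Quartile chi-square |
|---|---|---|---|
| 0 | 27% | 16% | 100% |
| 0.25 SD | 97% | 96% | 100% |
| 0.5 SD | 100% | 100% | 100% |

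A separate run of 600 replicates at c = 0 gave 23% (t-test) and 12% (rank test). The symmetric case is therefore dropped in 100 − 27 = 73% to 100 − 12 = 88% of datasets. At c = 0.25 SD the loss is 3 to 4% here, and about 3 to 6% allowing for simulation error. At N = 1,000 and c = 0.25 SD, the three tests keep 76%, 70% and 94%; at c = 0 the quartile test keeps 83%.

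**Step 3: correlated predictors with ordinary linear effects.** Log-odds = a + 0.15(x₁ + x₂ + x₃), pairwise correlation 0.8, 400 replicates:

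| | N = 1,000 | N = 2,000 | N = 3,000 |
|---|---|---|---|
| A given predictor passes alone | 67% | 92% | 98% |
| A given predictor passes in the joint model | 9% | 11% | 14% |
| All three fail in the joint model | 76% | 69% | 59% |

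The simulation error of the last figure is √(0.59 × 0.41/400) = 0.025. Across repeats the last row lies between about 57 and 80%. This loss needs no U-shape: it comes from requiring each predictor to be significant given the other two.

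**The case against.** The best defence is that the protocol names both univariate and multivariate analyses and does not fix the test, threshold, functional form or order. A plan may leave these to the SAP. Quartiles or splines would keep nearly all U-shapes at N = 2,500, and a multivariable analysis of all candidates recovers suppressed effects. The symmetric U is a knife-edge case, and its assumed effect is extreme: exp(0.5 × 9) is about 90 for the odds ratio at 3 SD against the mean. All of this stands. It limits how large a loss may be claimed, and missing detail on the test is not the complaint.

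It does not remove the point. The protocol itself decides that association with the outcome controls entry to the models. The multivariate step, which helps with suppression, is the one that can hurt correlated predictors. A stepwise procedure would tend to keep at least one of three such predictors, but none is described.

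Three stronger readings are tempting, and the documents support none of them:

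- **That the filter is univariate only and therefore removes all conditional effects.** The text names multivariate analyses too.
- **That PPV, SPV and SVV will be lost.** The documents give neither the shape of their effects nor their correlation. Calling them key features may signal an intention to retain them, although section 1.2.1 does not say so.
- **That about three quarters or more of non-linear predictors would be discarded.** That figure belongs only to the exactly symmetric case under a t-test or rank test.

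**Conclusion.** The point holds as a risk built into the stated sequence, not as a demonstrated loss. An outcome-based filter precedes the learners, SHAP ranks only its survivors, and nothing protects the parameters on which the study is built.

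The possible loss ranges from almost none (monotone effects, or quartile grouping at N = 2,500) to most datasets (a symmetric U or crossover effect under linear terms, or correlated predictors judged in a joint model). Where the study falls depends on the unstated form of the filter, the development sample size and the true effects. The correlated case is the most relevant to the key features, because it requires only ordinary linear effects; the correlation of 0.8 and log-odds of 0.15 remain assumptions.

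This is a cheap improvement worth making, not a flaw that invalidates the study.

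**What to change.** In section 1.2.1, replace the Feature Selection sentence along these lines:

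- Fix the candidate list without looking at the outcome, using clinical grounds, availability, missingness and near-zero variance.
- Always keep the cardiopulmonary interaction parameters on that list.
- Drop both the univariate and the multivariate significance steps as entry conditions. Do any selection or shrinkage inside cross-validation on the training data.
- Report univariate and multivariate associations for description only.

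This is about two sentences of text and needs no new data. The price is a longer candidate list and longer run time.

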2.1 Study Design

This single – center cohort study has two phases: retrospective and prospective.

The retrospective phase analyzed patient data from June 2019 to May 2024 to develop and validate machine learning models. The prospective phase, starting December 2025, will enroll eligible patients. It will collect preoperative, intraoperative, and postoperative data, including cardiopulmonary interaction parameters and clinical blood samples. This data will assess the model's and early warning system's accuracy and effectiveness.

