2.3 Sample Size and Calculation

This study will enroll 2,497 patients to ensure adequate statistical power for external model validation. In major liver surgery, ALI incidence is approximately 4.1%.

Performance Indicator	Hypothetical Value	Target 95% Confidence Interval Width (Corresponding Standard Error)	Sample Size: Number of Study Participants (Events) Required
-----------------------	--------------------	---	---

O/E	1	1 (0.245a)	390 (16)
Calibration Slope	1	0.2 (0.051)	2497 (103)
C-index	0.8	0.1 (0.0255)	1912 (79)
Standardized Net Benefit	0.53	0.2 (0.051)	2403 (99)

Assuming the linear predictor follows a skewed normal distribution, with an outcome event rate of 0.041. The required sample sizes, based on different model performance metrics, are shown above.

In summary, the minimum clinical sample size required for external model validation is 2,497 participants.

2.4 Inclusion Criteria:

- a. Aged ≥ 18 years; b. Scheduled for major liver surgery (e.g., resection of two or more liver segments, liver transplantation); c. Willing to participate and sign the informed consent form.

2.5 Exclusion Criteria:

- a. Patient refusal;
- b. Presence of comorbidities that may affect outcome assessment; c
- c. Incomplete recording of outcome measures;
- d. Failure to follow up postoperatively;
- e. Treating physician's judgment that the patient is unsuitable for inclusion;
- f. Participation in another study that may interfere with outcome assessment of this study.

2.6 Intervention Methods:

This study involves no therapeutic interventions for participants; only their clinical data and samples will be collected.

[figure not shown]

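### The simplified model is fixed at 20 features and reweighted with no link to the number of ALI events and no stated shrinkage, so it is likely to overfit unless the development cohort is large

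*Protocol*

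**What the plan says.** Protocol section 1.2.1 sets out a sequence. Features are screened by univariate and multivariate analyses, and six algorithms are trained on part of the data. SHAP values are computed for the best performer. The next instruction is to "Select the top 20 features based on SHAP values", after which feature weights are determined for the simplified model. The stated guard against overfitting is to "optimize parameters through cross-validation to prevent overfitting", and it belongs to the training step, before the SHAP ranking. An independent test set follows.

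On the development data, section 2.1 says "The retrospective phase analyzed patient data from June 2019 to May 2024 to develop and validate machine learning models". It gives no number of patients or ALI events.

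Section 2.3 gives the event rate ("In major liver surgery, ALI incidence is approximately 4.1" per cent) and sizes the prospective phase: "the minimum clinical sample size required for external model validation is 2,497 participants". The row that sets this number is "Calibration Slope", with the value 1 in the column headed "Hypothetical Value".

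**The concern.** Twenty is an absolute number. It does not depend on how many ALI events the retrospective cohort contains, and no performance criterion can lower it. At 4.1%, each 1,000 patients yield 1,000 × 0.041 = 41 events, or 41 / 20 = 2.05 per feature. Weights refitted to so few events, on features picked from the same data, tend to be too large. Predicted risks for new patients are then too extreme, and the calibration slope falls below 1.

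The early warning system in section 1.2.2 presents probabilities to clinicians, so calibration matters as much as ranking. The prospective phase takes its size from the calibration slope. A model locked with inflated weights would show this fault only after about 2,500 further patients, although it can be prevented at the development stage.

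**Working it through.** **Inputs from the protocol.** Event rate 0.041, C-index 0.8 (section 2.3); 20 features (section 1.2.1).

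**Assumptions.** Unpenalised regression with one parameter per feature; development size (not stated, so a range is shown); a normal linear predictor (section 2.3 assumes a skewed normal but gives no mean, SD or skew).

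**The plan's own figures.**
- O/E row: (1 − 0.041) / (0.041 × 0.245²) = 389.7, so 390. This agrees.
- C-index row: the Newcombe standard-error formula gives 1,914 against the stated 1,912. This agrees closely.
- Calibration-slope row: 2,497 was not reproduced. With SE 0.051 and C = 0.8, the skew-normal shapes tried need about 7,100 to 14,300 patients. That is a separate question about validation size and does not enter below.

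**Step 1: explained variation.** A normal linear predictor with mean −3.811 and SD 1.241 gives event rate 0.041 and C = 0.8. Its Cox-Snell R² is 0.0516. The maximum is 1 − exp{2(0.041 ln 0.041 + 0.959 ln 0.959)} = 0.2898. A more cautious assumption, 15% of the maximum, is 0.15 × 0.2898 = 0.0435.

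**Step 2: patients needed for expected shrinkage S = 0.90.** The formula is n = P / {(S − 1) ln(1 − R²/S)} with P = 20.
- R² = 0.0516: 20 / {−0.1 × ln(1 − 0.0516/0.9)} = 3,387 patients; × 0.041 = 139 events.
- R² = 0.0435: 20 / {−0.1 × ln(1 − 0.0435/0.9)} ≈ 4,040 patients; × 0.041 = 166 events.
- Skewed predictors with C = 0.8 gave R² between 0.0481 and 0.0561 (shapes −5 to 10). The same formula then gives about 3,640 and 3,110 patients, so the order of magnitude does not depend on the normal assumption.

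Section 1.2.1 also splits the data before training. If 70% were used for training (an assumption), 3,387 training patients would require 3,387 / 0.7 ≈ 4,840 in all.

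**Step 3: expected slope by development size** (same formula solved for S, P = 20).

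| Patients | Events | Expected slope (R² 0.0435 to 0.0516) |
|---|---|---|
| 1,000 | 41 | 0.69 to 0.73 |
| 2,000 | 82 | 0.82 to 0.84 |
| 2,497 | 102 | 0.85 to 0.87 |
| 4,000 | 164 | 0.90 to 0.91 |
| 5,000 | 205 | 0.92 to 0.93 |

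**Step 4: effect of selection.** The table counts 20 parameters only. The protocol selects them from a larger, unstated set. A simulation assumed 60 candidates (6 strong, 10 weak), true C about 0.79, ranking by ridge-coefficient size in place of SHAP, and an unpenalised refit of the top 20. Mean validation slopes were 0.41, 0.60, 0.68 and 0.75 at 1,000, 1,750, 2,500 and 3,400 patients. A second coding of the same design agreed to within 0.04.

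**Step 5: which remedy works.**
- *A shorter list alone.* With the sparse signal of step 4, the top 6 had better slopes (0.59, 0.82, 0.90, 0.97) and about the same C-index. With the signal spread evenly over 20 predictors and 1,000 patients, the top 6 had slope 0.48 against 0.46 for the top 20, and C-index 0.65 against 0.71. A further simulation put the C-index loss at 0.05 to 0.09. A short list is therefore a trade-off.
- *A penalty on the same 20.* A cross-validated penalty moved the median validation slope from 0.38–0.47 to 1.05–1.12 at 1,000 patients, and from 0.70–0.72 to 0.97–0.99 at 2,500. There was no loss of C-index under sparse or spread-out signal.

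**The case against.** **A contradiction with section 2.3.** A reader might infer that a 20-feature model conflicts with the planned slope of 1. The documents do not support this. The 1 is a hypothetical value used to set the width of a confidence interval. The calculation contains no feature count, and nothing there predicts or requires that the model reaches it. A slope below 1 would be a result that the validation is meant to measure.

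**Overfitting as a fact.** A reader might also divide the 103 events of section 2.3 by 20 and conclude that development has 5.15 events per feature. Those events belong to the validation sample. The development size, the candidate count and the form of the final model are not given. With about 4,000 or more development patients and few candidates, the expected slope reaches 0.90. The formula also does not carry over to a tuned random forest, support vector machine or neural network. This objection stands and makes the point conditional.

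**Safeguards are planned.** Cross-validation, a data split and an independent test set are all in section 1.2.1. But the cross-validation is attached to training the full model. Nothing applies it to the number of features or to the reweighting. A test set reveals overfitting and does not remove it.

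**A preset length is practical, and details may sit in a statistical analysis plan.** Both are fair. Cutting to 20 lowers complexity, and a fixed list suits a bedside tool. The finding is therefore not that tuning details are absent. The protocol itself fixes the number, whatever the events turn out to be.

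**Conclusion.** The point holds in conditional form. The protocol commits to 20 reweighted features without reference to the development events and without shrinkage. For an unpenalised regression at 4.1% incidence and C = 0.8, a development set below about 3,400 to 4,000 patients (139 to 166 events) is expected to give a validation slope below 0.90. Selection on the same data pushes it lower, to 0.41 at 1,000 and 0.68 at 2,500 patients in the step 4 simulation.

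The formula rests on the unpenalised fit, the assumed R² and one parameter per feature. The simulated values also rest on 60 assumed candidates and independent of any figure in the protocol. Neither shows that the model will overfit, because the cohort size and the algorithm are unknown. The result does not justify a fixed cap on parameters per 1,000 patients or a rule favouring the shortest list, since a shorter list can cost discrimination.

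**What to change.** In section 1.2.1:

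1. State the number of retrospective patients and ALI events available for development.
2. Change the top 20 to at most 20, with the number chosen by cross-validated log-loss and with both the screening and the SHAP ranking repeated inside the folds. If the features are chosen first on all the data, cross-validation takes the selection optimism for signal and the penalty comes out too weak.
3. Fit the simplified model with a cross-validated penalty, or multiply its linear predictor by an optimism-corrected shrinkage factor and re-estimate the intercept, before it is locked for the prospective validation.

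The cost is one or two sentences, more computing and possibly a shorter feature list. If the events are ample, 20 features can stand. Section 2.3 needs no change on this account.

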1.2.2 Construction and Clinical Validation of the Early Warning System

Construction of the Early Warning System

Expert System Development: Develop an ALI treatment expert system for the entire liver surgery process based on ML models. Integrate clinical guidelines, expert experience, and model predictions to form an ALI early warning system.

Logical Reasoning and Decision-Making Functions: Implement automatic logical reasoning and rapid clinical decision-making based on rules to provide real-time warnings and decision support for clinicians.

System Iteration and Optimization

Application of Information Fusion Technology: Use information fusion technology to integrate multi-source observational data, including vital signs, laboratory results, and imaging data, to enhance the accuracy and reliability of the early warning system.

System Optimization: Refine the early warning system based on clinical feedback and

actual application scenarios to improve system performance and user experience.

Clinical Validation and Evaluation

Expert Concept Validation Tests: Conduct concept validation tests for the iterated early warning system with clinical experts. Evaluate the system's probability predictions and perioperative suggestions, assessing dimensions such as consistency and acceptability through questionnaires.

Clinical Application Validation: Apply the early warning system in clinical practice, collect feedback from clinicians and patients, and evaluate the system's clinical value and effectiveness to further optimize its performance.

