2.8 Statistical Analysis Methods

Data will be analyzed using R or SPSS, with analyses including descriptive statistics, correlation analysis, and regression analysis.

3. Flowchart

4. Evaluation Criteria

Primary outcome measure: Incidence of ALI within 7 postoperative days.

ALI diagnosis currently uses the Berlin definition of acute respiratory distress syndrome (ARDS):

- Onset: Acute occurrence within one week of known injury or new/worsening respiratory symptoms;
- Chest imaging (X-ray or CT): Bilateral pulmonary opacities not fully explained by effusion, atelectasis, or nodules;
- Pulmonary edema cause: Respiratory failure not fully attributed to heart failure or fluid overload; if no related risk factors, objective tests (like Doppler echocardiography) are needed to exclude hydrostatic pulmonary edema;
- Oxygenation:

Mild: With CPAP/PEEP >5 cmH₂O, 200 mmHg <PaO₂ /FiO₂ <300 mmHg;

Moderate: With CPAP/PEEP >5 cmH₂O, 100 mmHg <PaO₂ /FiO₂ <200 mmHg;

Severe: With CPAP/PEEP >5 cmH₂O, PaO₂ /FiO₂ <100 mmHg. Opportunities for improved clinical trial designs in acute respiratory distress syndrome Wick, Katherine D et al.

The Lancet Respiratory Medicine, Volume 10, Issue 9, 916 – 924

Secondary outcome indicators include postoperative recovery status, hospitalization duration, and complication incidence, among others.

5. Safety Reporting and Adverse Event Management

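### One simplified model is planned for the whole surgical process and for real-time warnings, but no prediction time is set, so its measured performance need not be what a warning delivers

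*Protocol*

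**What the plan says.** All references are to the protocol.

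- **Candidate predictors (1.2.1, Data Collection).** Besides cardiopulmonary interaction parameters, the list has "preoperative baseline information (age, gender, weight, medical history") and "intraoperative information (surgery type, duration, anesthesia method, blood transfusion status), and postoperative information (complications, hospital stay, follow-up status").
- **Selection (1.2.1, Model Simplification).** From the best-performing algorithm the plan is to "Select the top 20 features based on SHAP values to create a" simplified risk model. Selection is not restricted by when an item becomes known.
- **Weights (1.2.1).** The next step is to "Determine the feature weights in the simplified model for the entire major liver surgery process to support clinical decision-making".
- **Use (1.2.2).** An expert system based on the machine learning models is "to provide real-time warnings and decision support for clinicians".
- **Outcome (section 4, Evaluation Criteria).** "Incidence of ALI within 7 postoperative days".
- **Evaluation (1.2.1).** The plan will "evaluate its predictive performance using metrics such as sensitivity, specificity, accuracy, and ROC curve".
- **Sample size (2.3).** External validation needs 2,497 participants (103 events) at an event rate of 4.1%. Each participant is counted once.

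The protocol states no prediction time, no rule for inputs not yet observed, no remaining horizon for a warning given after surgery, and no measure of performance over a patient's whole course of warnings.

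**The concern.** A risk model is defined by when it is used, what is known at that moment, and the period ahead that it covers. Here the predictors come from every stage and the use is continuous, but the outcome is a single window. Three problems follow.

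1. **Inputs.** Surgery duration and transfusion status do not exist before surgery. Complications, length of stay and follow-up status do not exist at the end of surgery either. A C-index obtained with all 20 features filled in need not be the one available when an early warning would be given.
2. **Horizon.** A probability of ALI from surgery to day 7 is not the risk that remains on day 3 or day 5 for a patient still free of ALI.
3. **Unit of evaluation.** A patient scored several times has several chances of a false warning. Specificity from one score per patient does not describe that experience.

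At stake is what the prospective phase can conclude. It is meant to assess the accuracy of both model and warning system, and good figures at one unstated time could be taken as figures for the whole process.

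**Working it through.** **Check of the plan's own figures (2.3).**

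- O/E row: N = (1 − φ)/(φ × SE²) = 0.959/(0.041 × 0.245²) = 390, as stated.
- C-index row: the Newcombe standard-error formula at C = 0.8 and φ = 0.041 gives 1,914 for SE 0.0255, against 1,912 stated.
- Events: 2,497 × 0.041 = 102.4, shown as 103.

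The two reproduced formulas use one prediction and one outcome per participant. The calibration-slope row did not reproduce under the skew-normal predictors tried, but its parameters are not given and nothing below depends on it.

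**Inputs by time of availability (1.2.1).**

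| Candidate item | Known before surgery | Known at end of surgery |
|---|---|---|
| Age, gender, weight, medical history | yes | yes |
| Surgery duration, transfusion during surgery | no | yes |
| Complications after surgery, hospital stay, follow-up status | no | no |

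One item from the second row among the 20 leaves the preoperative input incomplete. One from the third row leaves the end-of-surgery input incomplete too.

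**Remaining risk.** Let F(d) be the cumulative incidence by day d, with F(7) = 0.041. Among patients still free of ALI, the remaining risk is r(d) = (0.041 − F(d))/(1 − F(d)). If the 7-day probability is unchanged, average O/E = r(d)/0.041.

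Even onset, day 3: F = 0.041 × 3/7 = 0.01757, so r = 0.02343/0.98243 = 2.38% and O/E = 0.58. 
Even onset, day 5: F = 0.041 × 5/7 = 0.02929, so r = 0.01171/0.97071 = 1.21% and O/E = 0.29.

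The documents give no onset pattern, so a range is shown:

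| Assumed onset | O/E, day 3 | O/E, day 5 |
|---|---|---|
| Late-loaded (daily weights 1, 1, 2, 3, 4, 5, 6) | 0.82 | 0.51 |
| Even | 0.58 | 0.29 |
| Half of remaining onsets every 2 days | 0.30 | 0.10 |

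The direction is the same throughout, because r(d) falls below 4.1% once events have occurred. Only the size depends on the pattern.

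**Repeated warnings.** Take a patient without ALI and an assumed specificity of 90% per look. With k independent looks, the chance of no false warning is 0.9^k. For correlated looks it is the probability that k equicorrelated normal scores all stay below the cut-off.

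| Looks | Correlation 0 | 0.5 | 0.9 | 0.99 |
|---|---|---|---|---|
| 7 | 48% | 65% | 81% | 87% |
| 9 | 39% | 61% | 80% | 87% |

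Perfect correlation returns 90%. The number of looks, the specificity and the correlations are all assumptions.

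**Precision at later times.** With even onset and C held at 0.8, the same C-index formula (width = 3.92 × SE) gives:

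| Time | Patients at risk | Events left | C-index interval width |
|---|---|---|---|
| End of surgery | 2,497 | 102 | 0.087 |
| Day 3 | 2,453 | 59 | 0.115 |
| Day 5 | 2,424 | 29 | 0.161 |

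**The case against.** The strongest reply is that the protocol is underspecified here and not wrong. A reader might infer that one unchanging set of weights is laid down, that the model therefore cannot be scored before surgery, that it will over-predict more each day, and that false warnings will pile up unseen. The text does not go that far:

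- A single weight set is the natural reading of 1.2.1, but the sentence could also mean weights worked out across stages. Section 1.2.2 speaks of models in the plural, fuses several data sources and plans to refine the system.
- The 20 features are not yet known. Preoperative scoring fails only if a later item is selected and nothing is done about missing inputs.
- Over-prediction requires the 7-day probability to stay unchanged and to be read as remaining risk. Neither is stated, and updated inputs would move the output.
- Warnings come from rules that combine guidelines, expert experience and model predictions. No re-scoring schedule is given.
- The list of metrics is open, the warning system has its own broadly worded evaluation, and an SAP that is not shown may add detail.

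These replies remove the certainty and any fixed magnitude. They do not remove the point. The protocol does choose one simplified model for the whole process from predictors of every stage, uses it for real-time warnings, and sets one fixed outcome window. Refinement from clinical feedback does not define a prediction time or a horizon. The prediction time also determines what the 2,497-patient validation estimates, so it is more than a detail of analysis.

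**Conclusion.** The point holds in conditional form. As written, performance measured on the full feature set need not be the performance available at an earlier warning.

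- **Before surgery:** there is no complete input if any intraoperative or postoperative item is among the 20. This is likely, because selection ignores timing, but it is not certain.
- **After surgery:** an unchanged 7-day probability read as current risk over-predicts on average. O/E is about 0.58 at day 3 with even onset, and 0.30 to 0.82 over the patterns in the table.
- **Repeated warnings:** single-prediction specificity does not describe them. With 7 looks at 90%, patient-level specificity runs from 48% (independent looks) to 87% (correlation 0.99). This illustrates the range and does not forecast the system's specificity.

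The documents do not support saying that the system cannot work before surgery, or that it will over-predict by a known factor.

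**What to change.** 1. **Headline claim.** Name one prediction time (for example end of surgery) for the 2,497-patient performance claims. Limit that model's candidates to items recorded by then, include only patients still free of ALI, and predict ALI from then to day 7.
2. **Preoperative warnings.** If these are claimed, fit and report a separate model that uses preoperative items only.
3. **Later or repeated warnings.** Use the remaining window to day 7 as the target. One pooled landmark model with time since surgery as a term would do this, where time-stamped data allow. It is preferable to a separate model for each day, since only about 29 events remain at day 5 under even onset.
4. **Warning system.** Report patient-level sensitivity and specificity, counting any warning before onset as a positive.

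**Cost.** Items 1 and 2 need wording and extra model fits. Items 3 and 4 need time-stamped inputs, warnings and onset; section 2.7 gives no daily schedule of postoperative measurements, so availability must be confirmed. The C-index may be lower at earlier prediction times, and precision falls at later ones, as the last table above shows. The prediction time should be settled before the prospective validation data are analysed.
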